6.5. Safety and Tolerability Assessments

Safety and tolerability assessments include monitoring AEs; PEs; neurological examinations; vital signs and weight; ECGs; clinical laboratory analyses in blood and urine; MRIs; Sheehan-STS; and ADAs.

6.5.1. Adverse Events

All AEs and SAEs must be recorded and reported, regardless of cause or relationship, that occur after the participant signs informed consent and through the Part 1/Part 2 EOS or Safety Follow-up visit, whichever is later. Any unresolved AEs and SAEs will be followed up through satisfactory clinical resolution. Additionally, SAEs considered related to study drug which occur at any time should be reported by the investigator regardless of the AE/SAE collection window. Definitions describing what is and is not considered an AE are provided in [Section 7.1](#).

6.5.2. Concomitant Medications

All medication history and use of concomitant medications will be collected and recorded in the eCRF as detailed in [Section 5.6](#).

6.5.3. Demographics

Demographic information (year of birth, age, sex, race, ethnicity) will be recorded at screening, unless disallowed by local regulatory agencies.

For US, UK, and Canadian participants who will be performing the optional WLA, additional demographic information will be collected (ethnicity, number of years of education, first language, when they learned English [if English is not their first language], how long they have been speaking English consistently [if English is not their first language], country of birth, and year of immigration to Canada/United States/United Kingdom [if applicable]).

Alector is collaborating with the GENFI study, a group of research centers across Europe and Canada with expertise in familial FTD, and the ARTFL LEFFTDS Longitudinal Frontotemporal Lobar Degeneration (AllFTD) study, a study in the United States and Canada targeting most varieties of frontotemporal lobar degeneration (FTLD). As part of the GENFI and AllFTD

studies, all clinical trial participants will have the option of having a National Institute on Aging (NIA) Global Unique Identifier (GUID) generated. The GUID is a secure, random alphanumeric identifier. It can be used to match participants across studies and datasets without disclosing participants' Personal Identifying Information or Personal Health Information. The purpose of this GUID is to allow for the sharing of deidentified data and biospecimens between sponsors and GENFI and AllFTD.

For AL001-2 study participants who are also participating in the GENFI or AllFTD, they will have the option to have their NIA GUID collected by the investigational site personnel and recorded in the AL001-2 EDC system. For AL001-2 study participants who are not participating in GENFI or AllFTD, they will have the option for the investigational site personnel to assign a NIA GUID and recorded it in the AL001-2 EDC system.

6.5.4. Medical History

All relevant medical history, including history of current disease, other pertinent history, and information regarding underlying diseases will be recorded at screening prior to study drug administration in the eCRF.

A diagnostic characterization form will be completed in an EDC system for symptomatic participants only at screening, week 97 and week 197 (if applicable for symptomatic participants in the optional Part 2 OLE). It will also be completed for any asymptomatic participant who becomes symptomatic during the course of the study; for these participants, the diagnostic characterization form will be completed only at the first visit in which they exhibit clinical symptomatology and at all remaining study timepoints.

6.5.5. Physical Examinations

A complete PE includes evaluation of the head, eyes, ears, nose, and throat, and the cardiovascular, dermatological, musculoskeletal, respiratory, and gastrointestinal systems. Breast, genital, and rectal examinations are not required, unless warranted in the opinion of the health care provider. Limited examinations should include cardiovascular, respiratory, and gastrointestinal systems. Symptom-directed PEs may also include any other pertinent system as required. The examination will be performed by a physician or by a nurse practitioner or physician's assistant under the supervision of a physician.

Complete or limited or symptom-directed examinations will be performed at time points indicated in the Schedule of Assessments. For visits with study drug administration, this should be completed prior to the study drug infusion. Additional examinations may be completed as clinically indicated.

Record abnormalities observed at screening on the General Medical History and Baseline Conditions page of the eCRF. At subsequent visits, record new or worsened clinically significant abnormalities on the AE eCRF.

Height (cm) will be measured at screening.

6.5.6. Neurological Examinations

A complete neurologic examination should include the evaluation of consciousness, orientation, cranial nerves, motor and sensory system, coordination and gait, and reflexes. Limited or symptom-directed examinations will be performed at all other specified time points. A symptom-directed neurological examination should focus on the affected organ system or body area.

For visits with study drug administration, this should be completed prior to study drug infusion. Additional examinations may be completed as clinically indicated.

Record abnormalities observed at screening on the General Medical History and Baseline Conditions page of the eCRF. At subsequent visits, record new or worsened clinically significant abnormalities as AEs on the AE eCRF.

6.5.7. Vital Signs and Weight

Supine systolic and diastolic BP, pulse, body temperature, and respiratory rate will be recorded after the participant has been resting for ≥ 5 minutes in the supine position.

Pulse rate, BP, body temperature, and respiratory rate should be obtained per institutional practices.

Record abnormalities observed at screening on the General Medical History and Baseline Conditions eCRF. At subsequent visits, record new or worsened clinically significant abnormalities on the AE eCRF.

Weight (kg) will be collected at the same visits that vital signs are taken.

6.5.8. Electrocardiograms

Triplet 12-lead ECGs will be obtained after the participant has been in the supine position for ≥ 5 minutes.

Additional ECG monitoring must be performed during the treatment period if clinically indicated.

All ECGs will be analyzed from a clinical safety basis (without intensive QT analysis). The clinical significance of ECG changes will be determined by the investigator after review of the ECG report in relation to the participant's medical history, PE, and concomitant medications and documented in the eCRF.

6.5.9. Laboratory Assessments

Blood and urine samples that will be collected for clinical safety laboratory tests (chemistry, coagulation, hematology, urinalysis, serology, and pregnancy testing) are indicated in [Table 3](#).

For any laboratory test value outside the reference range that the investigator considers clinically significant, the investigator will follow the instructions in [Section 7.3](#).

Laboratory assessment analysis will be performed at a central laboratory, with the exception of urine pregnancy testing or medically indicated emergency laboratory tests which will be done at local laboratories.

Table 3: Laboratory Assessments

Chemistry	Coagulation	Hematology	Serology
Total bilirubin	PT	HbA1c	anti-HCV
Direct bilirubin	INR	Leukocytes	anti-HIV
Alkaline phosphatase	aPTT	Erythrocytes	HIV antigen
gammaGT		Hemoglobin	HBsAg
AST		Hematocrit	Total hepatitis B core antibody
ALT		Thrombocytes (platelets)	
LDH		MCV	
Creatine kinase		MCH	
Creatinine ^a		MCHC	
Urea		Partial automated differentiation:	
Uric acid		Lymphocytes	
Cholesterol		Monocytes	
HDL		Eosinophils	
LDL		Basophils	
Triglycerides		Neutrophils ^b	
Total protein		ANC ^b	
Albumin			
Glucose			
Bicarbonate			
Inorganic phosphate			
Sodium			
Potassium			
Calcium			
Chloride			
Magnesium			
Lipase			
Apolipoprotein B100			
		Urinalysis	Pregnancy Test
		Hemoglobin (blood urine)	Serum β -hCG or urine pregnancy test ^c
		Ketones	
		Glucose	
		Protein	
		Leukocyte esterase	
		Nitrite	
		pH	
		Specific gravity	
		Microscopic analysis ^d (sediment, erythrocytes, leukocytes, casts, crystals, epithelial cells, and bacteria)	

Abbreviations: ALT, alanine aminotransferase; ANC, absolute neutrophil count; aPTT, activated partial thromboplastin time; AST, aspartate aminotransferase; β -hCG, β -human chorionic gonadotropin; gammaGT, gamma glutamyl transferase; HBsAg, hepatitis B surface antigen; HCV, hepatitis C virus; HDL, high-density lipoprotein-cholesterol; HIV, human immunodeficiency virus; INR, international normalized ratio; LDH, lactate dehydrogenase; LDL, low-density lipoprotein-cholesterol; MCH, mean corpuscular haemoglobin; MCHC, mean corpuscular hemoglobin concentration; MCV, mean corpuscular volume; PT, prothrombin time.

^a Creatinine (and calculation of glomerular filtration rate).

^b ANC will be calculated at Screening only. Neutrophils will be assessed at all other time points.

^c All women of childbearing potential will have a serum pregnancy test at screening. Urine pregnancy tests will be performed at specified subsequent visits prior to study drug administration. If a urine pregnancy test is positive, it must be confirmed by a serum pregnancy test.

^d Microscopic examination of the sediment if blood, protein, leukocytes esterase, or nitrite are positive on the dipstick.

6.5.10. Sheehan Suicidality Tracking Scale

The Sheehan-STS (described in [Appendix 2](#)) is a brief scale designed to assess and monitor over time the core phenomena of suicidality. Any change in the Sheehan-STS score indicating the presence of suicidality should be immediately evaluated by the investigator and reported to the Medical Monitor. An AE should only be recorded if the investigator makes an evaluation and deems there to be suicidal ideation or behavior.

6.5.11. Anti-Drug Antibodies

Blood serum samples will be collected for determination of ADAs.

Additional ADA samples should be collected in participants with signs and symptoms of infusion-related reactions ([Section 5.1.2](#) and [Section 7.9](#)). A sample of blood should be obtained for serum PK and ADA assessment of AL001, and testing should be performed for C-reactive protein, tryptase, and Interleukin 6 (IL-6).

6.6. Pharmacokinetic Assessments

6.6.1. Serum Pharmacokinetic Samples

Blood serum samples will be collected for assessment of serum concentrations of AL001. All PK samples should be collected from the arm that is not used for the infusion on day of study drug administration.

6.6.2. Cerebrospinal Fluid Pharmacokinetic Samples

Cerebrospinal fluid samples will be assessed for concentration of AL001 in Part 1 only. See [Section 6.4](#) for details of CSF sampling.

6.7. Pharmacodynamic Biomarker Assessments

6.7.1. Progranulin Plasma Samples

Blood PGRN plasma samples will be collected for evaluation of levels of PGRN.

6.7.2. Cerebrospinal Fluid Pharmacodynamic Samples

Cerebrospinal fluid samples will be evaluated for levels of PGRN in Part 1 only. See [Section 6.4](#) for details of CSF sampling.

6.7.3. Whole Blood Samples

Whole blood samples will be collected for evaluation of levels of Sortilin in WBCs and for evaluation of other analytes in Part 1 only.

6.7.4. Exploratory Pharmacodynamic Biomarker Assessments

6.7.4.1. Other Exploratory Pharmacodynamic Biomarker Samples

Exploratory whole blood, plasma, and CSF PD biomarker samples will be collected for evaluation for neurodegeneration (e.g., neurofilament light chain [NfL], [REDACTED]), lysosomal function (e.g., cathepsins), and glial activity (e.g., YKL-40, IL-6), evaluation of messenger ribonucleic acid (mRNA) expression in peripheral cells, and to potentially evaluate levels of other analytes relevant to disease biology and response to AL001. CSF PD biomarker samples will be collected in Part 1 only.

6.7.4.2. Magnetic Resonance Imaging

MRI scans of the brain will be performed and centrally reviewed for assessment of safety, and for evaluation of global and regional brain volumes, volume of white matter hyperintensities, brain perfusion (measured by [REDACTED] MRI), fractional anisotropy, [REDACTED] [REDACTED].

Specific information regarding the collection and processing of MRI images will be provided in a separate manual.

6.8. Pharmacogenomic Assessments

A blood sample will be collected during Part 1 at screening for DNA extraction to enable analysis via WGS to identify common and rare genetic variants that are predictive of response to study drug, are associated with progression to a more severe disease state, are associated with susceptibility to developing AEs, or can increase the knowledge and understanding of disease biology.

Genomics is increasingly informing researchers' understanding of disease pathobiology. Whole genome sequencing provides a comprehensive characterization of the genome and, along with clinical data collected in this study, may increase the opportunity for developing new therapeutic approaches. Data will be analyzed in the context of this study but will also be explored in aggregate with data from other studies. The availability of larger datasets will assist in identification of important pathways, guiding the development of new targeted agents.

6.9. Clinical Outcome Assessments – Neurocognitive and Functional Tests

The following neurocognitive and functional tests (described in [Appendix 2](#)) will be performed. Neurocognitive and functional tests will be performed prior to study drug administration (if applicable) and prior to any stressful procedures (e.g., blood collections, imaging).

- Clinical Dementia Rating Dementia Staging Instrument PLUS National Alzheimer's Disease Coordinating Center Frontotemporal Lobar Degeneration Behavior and Language Domains (CDR[®] plus NACC FTLD)
- Frontotemporal Dementia Rating Scale (FRS)

- Clinical Global Impression of Improvement (CGI-I)
- Clinical Global Impression of Severity (CGI-S)
- Color Trails Test (CTT) Part 2
- Repeatable Battery for the Assessment of Neuropsychological Status (RBANS)
- WLA (US, UK, and Canadian participants who are proficient in English and who agree and are eligible to participate in the optional assessments only, refer to [Appendix 2](#)).

A tablet will be used to collect data for the electronic COAs. A few COAs will be completed on paper and entered into the eCRF. Specific information on the collection and data entry of neurocognitive and function tests will be provided in a separate manual. Adaptations to visits and procedures under the exceptional circumstance of COVID-19 pandemic are detailed in [Appendix 3](#).

Restrictions on when to stop the use of medications known to impair consciousness or cognition prior to COAs are provided in [Section 4.1.2](#).

6.10. Unscheduled Visits

Unscheduled visits may occur at any time while the participant is enrolled in the study.

6.11. Part 1 End of Treatment Visit

Participants who discontinue study drug prior to completing the 96-week Part 1 treatment period should be encouraged to complete all remaining scheduled assessment visits through Part 1 (including COAs, MRI, and CSF evaluations).

A Part 1 EOT visit will only be completed by participants who discontinue study drug but remain in Part 1 of the study and continue to perform all assessments ([Section 4.3.1.1](#)). Part 1 EOT assessments should be completed as soon as possible after the decision is made.

The EOT visit may be substituted by a scheduled study visit if it occurs within the same window.

6.12. End of Study Visit

6.12.1. Part 1 End of Study Visit

Participants who discontinue study drug and all assessments prior to completing the 96-week Part 1 treatment period ([Section 4.3.2](#)) will complete a Part 1 EOS visit as soon as possible after the decision is made. The Part 1 EOS visit may be substituted by a scheduled study visit if it occurs within the same window.

Participants who complete the 96-week Part 1 treatment period, at Week 97, will have the option to continue to receive AL001 in Part 2 (OLE) of the study. Participants who do not continue in Part 2 will complete a Part 1 EOS visit at the scheduled Week 97 timepoint. Participants who continue in Part 2 will complete the Week 97 visit and continue to Part 2 (Week 101).

6.12.2. Part 2 End of Study Visit

Participants who discontinue study drug and/or all assessments prior to completing the 96-week Part 2 treatment period ([Section 4.4.1](#)) will complete a Part 2 EOS visit as soon as possible after the decision is made. The Part 2 EOS visit may be substituted by a scheduled study visit if it occurs within the same window.

At Week 197, participants who complete the 96-week Part 2 OLE period will complete a Part 2 EOS visit at the scheduled Week 197 timepoint.

6.13. Safety Follow-up Visit

A Safety Follow-up visit will be performed 10-weeks following the last dose of AL001. The Safety Follow-up visit may be substituted by a scheduled visit if it occurs within the same window.

7. ADVERSE EVENTS

The investigator's assessment of an AE's relationship to study drug is part of the documentation process, but it is not a factor in determining what is or is not reported in the study. If there is any doubt as to whether a clinical observation is an AE, the event should be reported.

7.1. Definitions of Adverse Events

The investigator is responsible for reporting all AEs that are observed or reported during the study, regardless of their relationship to study drug or their clinical significance.

An AE is defined as any untoward medical occurrence in a participant enrolled into this study regardless of its causal relationship to study drug. Participants will be instructed to contact the investigator at any time after informed consent signature if any symptoms develop. Study participants should be instructed to report all AEs to the investigator. All AEs must be appropriately documented in the participant's original source documents and on the eCRFs. Investigators should report the diagnosis rather than list symptoms, whenever possible.

An AE does not include the following:

- Elective medical or surgical procedures planned prior to the start of study treatment (e.g., hip replacement surgery) that did not result from a worsening of a previous condition. The condition that led to the procedure may be an AE and must be reported.
- Pre-existing diseases, conditions, or laboratory abnormalities present or detected at the screening visit that do not worsen.
- Situations where an untoward medical occurrence has not occurred (e.g., hospitalization for study drug administration per institutional guidelines, elective surgery, social and/or convenience admissions).
- Overdose without clinical sequelae.
- Any medical condition or clinically significant laboratory abnormality that has an onset date before the consent form is signed and that is not related to a protocol-associated procedure is not an AE. It is considered to be a pre-existing medical condition and should be documented on the medical history eCRF. However, deterioration of a medical condition or new or worsened clinically significant abnormality during the study should be reported as an AE.
- Any AE that began during the Phase 1 study (AL001-1) and was ongoing at the time of enrolling in this study (AL001-2) will not be considered an AE, but medical history.

Adverse events resulting from concurrent illnesses, reactions to concurrent illnesses, reactions to concurrent medications, or progression of disease states must also be reported in the established time frames.

A treatment emergent adverse event (TEAE) is defined as any event not present before exposure to study drug, or any event already present that worsens in either intensity or frequency after exposure.

7.2. Serious Adverse Events

An SAE is defined as any AE that fulfills one or more of the following criteria:

- Results in death
- Is immediately life-threatening
- Requires inpatient hospitalization or prolongation of existing hospitalization
- Results in persistent or significant disability/incapacity
- Is a congenital anomaly/birth defect
- Is an important medical event that may jeopardize the participant or may require medical intervention to prevent one of the outcomes listed above

Important medical events that may not result in death, be life-threatening, or require hospitalization may be considered SAEs when, based upon appropriate medical judgment, they may jeopardize the participant or may require medical or surgical intervention to prevent one of the outcomes listed in this definition. Examples of such medical events include allergic bronchospasm requiring intensive treatment in an emergency room or at home, blood dyscrasias or convulsions that do not result in inpatient hospitalization, or the development of drug dependency or drug abuse.

An AE is considered “life-threatening” if, in the opinion of either the Investigator or the Sponsor, its occurrence places the participant at immediate risk of death. It does not include an AE that, had it occurred in a more severe form, might have caused death.

Social hospitalization, defined as inadequate family support or care at the participant’s primary residence resulting in participant hospitalization, will not be considered an SAE.

7.3. Eliciting and Documenting Adverse Events

At every study visit, participants will be asked a standard, nonleading question to elicit any medically related changes in their well-being. They will also be asked if they have been hospitalized, had any accidents, used any new medications, or changed concomitant medication regimens (prescription drugs, herbal products, vitamins, minerals, vaccines, topical medications, and over-the-counter medications).

Laboratory test values or investigational findings (e.g., findings on ECGs, imaging, or examination) outside the normal reference range that meets the following criteria should be reported as an AE: (1) is confirmed and the investigator considers clinically significant, or (2) requires a participant to be discontinued from the study, or (3) requires a participant to receive treatment. Abnormal laboratory test values or investigational findings reported as AEs

should be followed until satisfactory clinical resolution, participant withdrawal of consent, loss to follow-up, or death, whichever comes first.

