4.3.1. Part 1 (Treatment Period)

4.3.1.1. Withdrawal from Study Drug (Part1)

A participant may be discontinued from study drug at any time if the participant or the investigator feels that it is not in the participant's best interest to continue. The following is a list of possible reasons for study drug discontinuation:

1. Participant is noncompliant with the protocol
2. Participant is lost to follow-up
3. Participant withdraws consent
4. Participant has a serious or intolerable AE that, in the investigator' opinion, requires withdrawal from the study drug
5. Serum aminotransferase levels (ALT or AST) $>3 \times$ ULN AND total bilirubin $>2 \times$ ULN without an alternative explanation
6. Anaphylaxis
7. Infusion-related or injection-related reaction despite adequate premedication for an initial occurrence of a moderate to severe infusion-related reaction ([Section 5.1.2](#)) or if the participant experiences any of the following events: mucosal tissue involvement, airway compromise, or symptomatic hypotension with systolic blood pressure <90 mm Hg measured in the supine position
8. Occurrence of an intercurrent illness that, in the investigator's opinion, will affect assessments of clinical status or safety to a significant degree
9. Use of a nonpermitted concomitant medication per [Section 4.1.2](#) (as appropriate)
10. Pregnancy
11. Discretion of the investigator

If a participant is withdrawn from study drug due to an AE or SAE, the participant will be followed up by the investigator until the abnormal parameter or symptom has resolved or stabilized (if applicable). The investigator has the responsibility for all decisions regarding participant safety. It is recommended that the investigator consult with the Medical Monitor prior to removing the participant from study drug for any reason except participant withdrawal of consent and in case of medical emergency. If a participant is discontinued because of an AE or SAE, the event will be followed up until it is resolved. Any participant may withdraw his or her consent at any time.

All participants who discontinue study drug prior to the completion of the Part 1 96-week treatment period should be encouraged to complete all remaining scheduled assessment visits through the Part 1 treatment period (Week 97). Study staff will follow-up to aid in this goal.

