The reason for the participant's early discontinuation of study drug will be specified in the participant's source documents and on the eCRF. A Part 1 End of Treatment (EOT) visit will be completed by participants who discontinue the study drug but remain in the study and continue to perform assessments. Part 1 EOT assessments should be completed as soon as possible after the decision is made. A Safety Follow-Up visit will be performed 10 weeks after their last study drug administration. The Safety Follow-up visit may be substituted by a scheduled visit if it occurs within the same window.

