1.1. Objectives and Endpoints

Table 1: Part 1 (Treatment Period): Study Objectives and Endpoints

	Objective(s)	Endpoint(s)
Primary	The primary objective of the treatment period of the study is to evaluate the safety and tolerability of IV administration of AL001 over 96 weeks in asymptomatic and symptomatic carriers of a GRN mutation causative of FTD and in symptomatic carriers of a C9orf72 mutation causative of FTD.	Primary Safety Endpoints: To assess the potential effect of cumulative exposure on the safety profile of AL001, the following will be evaluated by dose, such as by using tertiles of the actual dose (normalized to weight) received: 
• Incidence, nature, and severity of AEs and SAEs• Incidence of treatment discontinuations and study discontinuations due to AEs• Physical examination abnormalities• Neurological examination abnormalities• Changes in vital signs from baseline over time• Changes in ECGs from baseline over time• MRI abnormalities after dosing relative to baseline• Changes in clinical laboratory tests from baseline over time• Sheehan Suicidality Tracking Scale (Sheehan-STS)• Incidence of ADAs to AL001
Secondary	The secondary objectives of the treatment period of the	

	
study are to evaluate the effect of IV administration of AL001 over 96 weeks in asymptomatic and symptomatic carriers of a GRN mutation causative of FTD and in symptomatic carriers of a C9orf72 mutation causative of FTD on the following:
	
	
Secondary PK Objective:
 
 • PK 	
Secondary PK Endpoints:
 
 • Serum concentration of AL001 at specified time points • AL001 PK parameters (if data permit) ◦ C_{max} ◦ C_{trough} ◦ AUC_{ss}
	
Secondary PD Biomarker Objectives:
 
 • Longitudinal plasma and CSF PGRN concentration levels • Longitudinal levels of Sortilin in WBCs 	
Secondary PD Biomarker Endpoints:
 
 • The overall change from baseline in PGRN in CSF • The overall change from baseline in PGRN in plasma • The overall change from baseline in Sortilin in WBCs in plasma

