6.2. Clinical Laboratory Evaluations

Blood and urine samples that will be collected for clinical safety laboratory tests (chemistry, coagulation, hematology, urinalysis, serology, and pregnancy testing) are indicated in [Table 8-1](#).

Laboratory assessment analysis will be performed at a central laboratory, with the exception of urine pregnancy testing which will be done at local laboratories.

Hematology, coagulation, serum chemistry, and urinalysis will be performed at the timepoints identified in [Appendix 14.1](#), [Appendix 14.2](#), [Appendix 14.4](#) and [Appendix 14.5](#). Additionally, unscheduled testing may be done during the study if medically indicated.

Abnormal clinical laboratory values will be flagged as either high or low (or normal or abnormal) based on the reference ranges for each laboratory parameter. The investigator will determine whether any of the abnormally high or low results are clinically significant or not clinically significant. Any clinically significant results will be entered into the eCRF as AEs, however the attribution of clinical significance will not be available in the data.

Actual results and change from baseline values for hematology, coagulation, serum chemistry, and urinalysis tests will be summarized by visit using descriptive statistics.

Shift from baseline in hematology, coagulation, serum chemistry, and urinalysis tests results relative to the reference range will be summarized by visit using the frequency count and percentage of participants in each category.

Refer to Section 4 for the definition of baseline.

All laboratory test results will be presented in data listings.

Table 8-1 Laboratory Assessments

Chemistry	Coagulation	Hematology	Serology
Total bilirubin	PT	HbA1c	anti-HCV
Direct bilirubin	INR	Leukocytes	anti-HIV
Alkaline phosphatase	aPTT	Erythrocytes	HIV antigen
gammaGT		Hemoglobin	HBsAg
AST		Hematocrit	Total hepatitis B core antibody
ALT		Thrombocytes (platelets)	
LDH		MCV	
Creatine kinase		MCH	
Creatinine ^a		MCHC	
Urea			
Uric acid			
Cholesterol			
HDL			
LDL			
Triglycerides			
Total protein			
Albumin			
Glucose			
Bicarbonate			
Inorganic phosphate			
Sodium			
Potassium			
Calcium			
Chloride			
Magnesium			
Lipase			
Apolipoprotein B100			
	Urinalysis		Pregnancy Test
	Hemoglobin (blood urine)		Serum β-hCG or urine pregnancy test ^c
	Ketones		
	Glucose		
	Protein		
	Leukocyte esterase		
	Nitrite		
	pH		
	Specific gravity		

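### Protocol 7.3 makes a test finding an AE if it ends study participation but not if it stops AL001, and asks for an undefined confirmation, so such findings may be recorded inconsistently

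*Protocol*

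**What the plan says.** Protocol 7.3 gives three criteria for reporting an out-of-range test value or investigational finding as an AE. The first two are "1) is confirmed and the investigator considers clinically significant, or (2) requires a participant to be discontinued from the study". The third covers findings for which treatment has to be given. For laboratory values judged clinically significant, Protocol 6.5.9 says "the investigator will follow the instructions in" Section 7.3.

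Part 1 treats stopping drug (4.3.1.1) and leaving the study (4.3.2) as separate events. An End of Treatment visit is defined for "participants who discontinue the study drug but remain in the study and continue to perform assessments", and those who stop drug "should be encouraged to complete all remaining scheduled assessment visits through the Part 1 treatment period (Week 97"). The reasons for stopping drug in 4.3.1.1 include a combined aminotransferase and bilirubin criterion (item 5). It is listed apart from a serious or intolerable AE (item 4), and no repeat test is mentioned.

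Other sections set a different recording rule. Protocol 6.5.7, on vital signs, reads "At subsequent visits, record new or worsened clinically significant abnormalities on the AE eCRF"; 6.5.5 and 6.5.6 say the same for physical and neurological examinations. SAP 6.2 says of laboratory tests: "Any clinically significant results will be entered into the eCRF as AEs". It adds that the clinical-significance judgement will not be available in the data.

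The primary safety endpoints in SAP 1.1 and Protocol Table 1 include "Incidence of treatment discontinuations and study discontinuations due to AEs". SAP 6.1.5 tabulates treatment-emergent AEs leading to study drug discontinuation by system organ class and preferred term.

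**The concern.** The recording rule and the endpoint do not match. The endpoint and the SAP 6.1.5 table count AEs that stop the drug, but 7.3 names only findings that end study participation. Because Part 1 encourages participants who stop drug to stay, the omitted event is the one the protocol expects to see.

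The confirmation condition is a second mismatch. A site following 6.5.9 and 7.3 may hold back a clinically significant laboratory value until it is confirmed, while SAP 6.2 assumes that every such value is already on the AE page. Because the laboratory significance call is not kept in the data, the analysis cannot recover it afterwards.

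At stake are the incidence of AEs and of AE-related drug discontinuation, both primary endpoints in a single-arm study of about 40 participants at about 13 sites. Any finding lost this way lowers the count, and no control arm exists in which a similar loss would offset it.

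**Working it through.** **1. The 7.3 criteria applied to Part 1 cases.** In each case a finding leads the investigator to stop AL001. Confirmed is taken to mean repeated; the protocol does not define it, so this is an assumption.

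| Case | (1) Confirmed and clinically significant | (2) Requires leaving the study | (3) Requires treatment | Meets 7.3? |
|---|---|---|---|---|
| A. Repeated, judged significant, untreated, stays | yes | no | no | yes |
| B. Not repeated, untreated, also has to leave the study | no | yes | no | yes |
| C. Not repeated, treated, stays | no | no | yes | yes |
| D. Not repeated, untreated, stays in follow-up | no | no | no | no |

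B and D differ only in whether the participant remains in follow-up. Item 5 of 4.3.1.1 can produce case D, because it lets a laboratory result stop the drug without asking for a repeat. Part 2 has one withdrawal list covering drug and assessments together (4.4.1), so this gap belongs to Part 1.

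**2. The confirmation condition, section by section.**

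| Place | Type of finding | Confirmation asked for? |
|---|---|---|
| Protocol 7.1 | any clinically significant abnormality, new or worsened | no |
| Protocol 6.5.5, 6.5.6, 6.5.7 | physical, neurological, vital signs | no |
| Protocol 8.4.2.4 | MRI changes | no |
| SAP 6.2 | laboratory | no |
| Protocol 7.3 | laboratory, ECG, imaging, examination | yes |
| Protocol 6.5.9 | laboratory | yes, by reference to 7.3 |

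Examination, vital-sign and MRI findings each have a specific instruction that does not ask for confirmation. Laboratory values are sent to the rule that does, so the conflict falls mainly on them.

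**3. Where a case D laboratory value still appears if no AE is recorded.** The value is listed and contributes to the by-visit summaries and shift tables (SAP 6.2). The reason for stopping drug is on the eCRF (4.3.1.1) and in disposition (Protocol 8.4.1.1, SAP 3.1). It is absent from the AE tables (SAP 6.1.1) and from the table of AEs leading to study drug discontinuation (SAP 6.1.5), because there is no AE term to tabulate.

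**4. The plan's own figure.** Protocol 8.1 gives the chance of at least one clinically significant associated finding in 40 participants, 1 − (1 − p)^40:

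- p = 0.1%: 3.9%
- p = 1%: 33.1%
- p = 5%: 87.1%
- p = 10%: 98.5%

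All four reproduce. They take every finding as recorded. The documents give no share of findings that would fail 7.3, so no corrected figure can be calculated.

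**The case against.** The strongest reply is that 7.3 says which findings should be reported, not that all others must be left out. Section 7.5 sends the reader to 7.1 for what is and is not an AE. Section 7.1 asks for all AEs whatever their clinical significance, and its exclusions do not mention unconfirmed results. The opening of Section 7 says to report in case of doubt. An investigator who stops AL001 under item 5 would probably judge the result clinically significant, and 4.3.1.1 itself speaks of following an abnormal parameter after withdrawal for an AE. All of this stands, and it makes certain loss an untenable reading. It does not remove the conflict: 6.5.9 sends laboratory values to 7.3 rather than 7.1, and a site applying the specific rule need feel no doubt.

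Two stronger inferences are tempting. A reader might conclude that a finding failing 7.3 reaches no other table as clinically significant. That is wrong for ECGs: clinical significance is documented in the eCRF (Protocol 6.5.8), and SAP 6.4 summarises shifts in it. Safety MRI results are listed (SAP 6.8). The SAP 6.2 statement about the missing significance call concerns laboratory values only.

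A reader might also conclude that a transient finding can never be confirmed, because scheduled chemistry after Week 13 of Part 1 is 12 weeks apart and ECGs about 24 weeks apart. Unscheduled visits are allowed at any time (Protocol 6.10), SAP 6.2 allows unscheduled tests if medically indicated, and 6.5.8 requires additional ECGs when clinically indicated.

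**Conclusion.** The point holds as a conflict between recording rules that bears on primary safety counts. In Part 1, an unconfirmed, untreated finding that stops AL001 while the participant stays in follow-up meets no 7.3 criterion, so whether it becomes an AE may depend on which section the site follows. Separately, a clinically significant laboratory value that is not confirmed is an AE under 7.1 and SAP 6.2 but can fail criterion (1). What may be lost is AE and AE-discontinuation counts, not the underlying data.

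A reader might try to size this by thinning the plan's detection probability, 1 − (1 − p × c)^40, where c is the share of findings recorded. At p = 5%, an assumed c of 0.75 gives 78.3% and an assumed c of 0.50 gives 63.7%, against 87.1%. The documents do not support using these as estimates. They give no value for c, and the examples in Protocol 8.1 are drug-related SAEs and drug-related AEs leading to drug discontinuation. Those include symptomatic events, which the test-finding rule does not govern.

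The conclusion rests on reading confirmed as repeated, and on some sites treating 7.3 as the operative rule for laboratory values.

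**What to change.** 1. In Protocol 7.3, extend criterion (2) to a finding that leads to discontinuation of study drug or of the study.
2. Reconcile criterion (1) with Protocol 7.1, 6.5.5 to 6.5.7 and 8.4.2.4 and with SAP 6.2, so that one recording rule on confirmation applies. The simplest route is to drop the confirmation condition. If it is kept, define it and carry it into the other sections.
3. In the SAP, reconcile the recorded reasons for stopping study drug against the AE page and query any safety-related stop with no AE record. Do not reclassify such stops automatically: that would override the investigator's judgement and leave stops with no term to tabulate. This step also reaches participants who stopped before 7.3 is changed.

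The cost is a few words in each document and one reconciliation listing before database lock. The downside is slightly higher AE counts, including a few unrepeated values. The change concerns recording only; the criteria for stopping AL001 stay as they are.
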